14.6. Secondary Analyses

The secondary analyses will be conducted on Intent-to-Treat populations to establish superiority and Per-protocol populations for non-inferiority.

CLUE Vision score – (S1)

CLUE vision scores at 1-week follow-up will be analyzed using a linear mixed effect model. This model will include the experimental design factors: sequence of lens wear, lens wearing period, lens type and the interaction between lens type and lens wearing period as fixed effects. Baseline characteristics known of importance such as age and gender will be included as fixed covariates. Site will be included as random effects (G-side). The covariance of residuals between of the same subject (R-side) across period will be modeled using either homogenous compound symmetry (CS) or unstructured (UN) covariance structure. The structure that returns the lowest finite sample corrected Akaike's Information criterion¹⁰ will be selected as the structure that best fits the model. The Kenward and Roger method will be used for the calculation of the denominator degree of freedom¹¹.

The null and alternative hypotheses for superiority of CLUE Vision for the Test (AO1DfA) minus Control (AO1D) is as follows:

$$H_0: \Delta \leq 0.0$$
$$H_A: \Delta > 0.0$$

where Δ is the least-square means (LSM) difference between the Test and Control lens (Test minus Control). Superiority for the Test to the Control lens will be established on ITT population if the lower bound of the 95% two-sided confidence interval (CI) for least squares mean (LSM) difference (Test - Control) of CLUE Vision score is greater than 0.

Visual Performance (HLHC logMAR) – (S2)

The comparison of Monocular distance visual performance of HLHC in logMAR scale between the Test (AO1DfA) to the Control (Spectacles) will be analyzed using a similar linear mixed effect model described in the primary analysis above. Since this endpoint for the Test lens (AO1DfA) will be collected before or after the Control (Spectacles) and no carryover effect is expected in objective visual performance, the lens wearing period can be defined accordingly.

The null and alternative hypotheses for non-inferiority of Test lens (AO1DfA) relative to Control (Spectacles) are as follows:

$$H_0: \Delta > 0.05$$
$$H_A: \Delta \leq 0.05$$

where Δ is the mean difference in logMAR between Test lens and Control lens (Test minus Control). Non-inferiority will be declared on Per-protocol population if the upper bound of the (1- α) two-sided confidence interval of the mean difference between Test and Control is less than 0.05. The α is the Type I error derived from Gatekeeping strategy and α -propagation in Section 14.4. If the non-inferiority is established, superiority will be declared

Clinical Study Protocol

Johnson & Johnson Vision Care, Inc.

if the upper bound of the confidence interval of the mean difference between Test and Control is less than 0.0.

Contact Lens Preference – (S3)

Contact lens preference question will be analyzed using a baseline-category logistic model, where the response of the Control lens preference is the baseline category. This model will include the experimental design factors: sequence of lens wear, lens wearing period, lens type and the interaction between lens type and lens wearing period as fixed effects. Baseline characteristics known of importance such as age and gender will be included as fixed covariates.

The null and alternative hypotheses for superiority of Test (AO1DfA) lens relative to Control (AO1D) are as follows:

$$H_0: \Delta \leq 1.0$$
$$H_A: \Delta > 1.0$$

where Δ is the odds of the preference for the Test to the preference for the Control (Test divided by Control). Superiority for the Test to the Control lens will be established on ITT population if the lower bound of the $(1 - \alpha)$ % two-sided confidence interval (CI) for least squares mean (LSM) odds (Test divided by Control) of the contact lens preference is greater than 1.0. The α is the Type I error derived from Gatekeeping strategy and α -propagation in Section 14.4.

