2.3. Hypotheses

Primary Hypothesis

1. After 1 week of wear, monocular HLHC VA for correction with AO1DfA lenses will be superior to that for mean sphere correction with AO1D spherical lenses.

Secondary Hypotheses

1. After 1 week of wear, the mean CLUE vision score for binocular correction with AO1DfA lenses will be superior to that for binocular mean sphere correction with AO1D spherical lenses.
2. After 1 week of wear HLHC VA for correction with AO1DfA lenses will be non-inferior to that for correction with subjects' habitual spectacles, using a non-inferiority boundary of -0.05 logMAR.
3. After 1 week of wear, subjects will have greater overall preference for binocular correction with AO1DfA lenses over AO1D spherical lenses.

The primary hypothesis must be met for the study to be considered successful.

Clinical Study Protocol

Johnson & Johnson Vision Care, Inc.

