14.4. Level of Statistical Significance

The following graphical Gatekeeping strategy¹² will be used to control the overall study-wise two-sided type I error rate $\alpha=5\%$. The primary hypothesis will be conducted with the two-sided type I error rate of $\alpha=5\%$. If primary hypothesis is met, the first secondary hypothesis will be conducted with $\alpha=5\%$. If first secondary hypothesis (S1) is met, the second and third secondary hypothesis will be conducted with the α -propagation proposed in Figure 2 which is also the Holm procedure. For exploratory analyses, each analysis is conducted with two-sided type I error rate $\alpha=5\%$.

Clinical Study Protocol

Johnson & Johnson Vision Care, Inc.

Figure 2: Gatekeeping strategy and α -propagation, P1 – Primary hypothesis and S1-3 – the first to third secondary hypothesis defined in section 2.3.

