14.5. Primary Analysis

The primary analyses will be conducted on Intent-to-Treat populations to establish superiority.

Visual Performance (HLHC logMAR)

Monocular distance visual performance of HLHC in logMAR scale will be analyzed using a linear mixed effect model. This model will include the experimental design factors: sequence of lens wear, lens wearing period, lens type and the interaction between lens type and lens wearing period as fixed effects. Baseline characteristics known of importance such as age and gender will be included as fixed covariates. Site will be included as random effects (G-side). The covariance of residuals between of the same subject (R-side) across period will be modeled using either homogenous compound symmetry (CS), heterogeneous compound-symmetry (HCS) or unstructured (UN) covariance structure. The structure that returns the lowest finite sample corrected Akaike's Information criterion¹⁰ will be selected as the structure that best fits the model. The Kenward and Roger method will be used for the calculation of the denominator degree of freedom¹¹.

The null and alternative hypotheses for superiority of Test (AO1DfA) lens relative to Control (AO1D) are as follows:

$$H_0: \Delta \geq 0.0$$
$$H_A: \Delta < 0.0$$

where Δ is the mean difference in logMAR between Test and Control lens (Test minus Control). Superiority for the Test to the Control lens will be established on ITT population if the upper bound of the 95% two-sided confidence interval (CI) for least squares mean (LSM) difference (Test - Control) of HLHC logMAR is less than 0.

Clinical Study Protocol

Johnson & Johnson Vision Care, Inc.

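### Section 14.6 lets superiority over spectacles be declared after non-inferiority, if the interval lies below zero, without any condition on S3; this reuses alpha that Holm passes to S3, so the section 14.4 error control does not cover the claim

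*Combined protocol and SAP*

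**What the plan says.** Section 14.4 sets out a gatekeeping scheme to "control the overall study-wise two-sided type I error rate" at 5%. P1 is tested first, then S1. If both are met, S2 and S3 share alpha by the propagation "proposed in Figure 2 which is also the Holm procedure". The Figure 2 caption limits the graph to P1 and "the first to third secondary hypothesis defined in section 2.3".

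In section 2.3 the spectacle comparison is S2 and is worded as non-inferiority only: "HLHC VA for correction with AO1DfA lenses will be non-inferior to that for correction with" the subjects' own spectacles. The synopsis words it the same way but lists it third. Holm treats the two hypotheses alike, so the order does not matter here.

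The S2 text in section 14.6 judges non-inferiority on the per-protocol population, using an interval whose level comes from the gatekeeping step. It then adds: "If the non-inferiority is established, superiority will be declared" "if the upper bound of the confidence interval of the mean difference between Test and Control is less than 0.0". Superiority therefore has two conditions: non-inferiority met, and the interval wholly below zero. S3 is not mentioned, the interval level is not restated, and the step is not labelled exploratory.

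On populations, section 14.6 opens with a general rule: "The secondary analyses will be conducted on Intent-to-Treat populations to establish superiority and Per-protocol populations for non-inferiority".

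**The concern.** Moving from non-inferiority to superiority on one interval costs no alpha when nothing else draws on that alpha. Here something else does. Under Holm, rejecting S2 releases its share so that S3 can be tested at the full 5%. Section 14.6 leaves the same share available for superiority over spectacles, whatever happens to S3. Two true nulls (no preference, no acuity advantage over spectacles) can then both be tested with alpha that the scheme provides only once.

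At stake is the status of one sentence in the study report. Superiority over spectacles could be presented as a secondary result under study-wise control when the plan's own scheme does not provide that control. The same sentence also leaves the analysis population open: the general rule gives superiority to ITT, while the interval referred to follows directly on the per-protocol one.

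**Working it through.** **Inputs.**
- Study-wise two-sided alpha 5%, Holm on S2 and S3: section 14.4.
- Margin 0.05 logMAR: sections 2.3 and 14.6.
- SD 0.09, N = 153, ICC 0.3 to 0.5: Table 10 (its inputs only, not its power values).
- Benchmark of 2.5% in the tested direction: inferred from section 14.5, where superiority on P1 "will be established on ITT population if the upper bound of the 95% two-sided confidence interval" lies below zero for a one-directional null. Section 14.4 does not state this figure.
- Correlation between the spectacle and preference tests: not in the documents. Assumed, range 0 to 0.8.
- P1 and S1 are taken as already met.

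**Step 1: the plan's own figure.** The Holm start gives 0.025 + 0.025 = 0.05 two-sided, or 0.0125 + 0.0125 = 0.025 in the tested direction. For S2 and S3 alone the stated control is reproduced.

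**Step 2: how readily S2 passes.** SE = 0.09 × √(2(1 − ICC)) / √153 = 0.00861, 0.00797 and 0.00728 for ICC 0.3, 0.4 and 0.5. If toric truly equals spectacles, the margin lies 0.05/0.00861 = 5.8 standard errors away at ICC 0.3, and further at the higher ICCs. S2 is then rejected, correctly, almost every time, and S3 is tested at 0.025 in its direction.

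**Step 3: add the superiority claim.** At the S2 level (97.5% interval) superiority has 0.0125 in the tested direction. With preference null and a true difference of 0:
- Independent tests: 0.025 + 0.975 × 0.0125 = 0.0372.
- Bound for any correlation: 0.025 + 0.0125 = 0.0375.
- If superiority is read from a 95% interval: 1 − 0.975² = 0.0494, bound 0.05.

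**Step 4: simulation.** 4,000,000 trials per setting, ICC 0.3 to 0.5, using the 97.5% interval, or the 95% interval if S3 is rejected first. Chance of at least one false claim:

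| Correlation | S2-level interval | 95% interval | Superiority only after S2 and S3 |
|---|---|---|---|
| 0 | 3.71-3.73% | 4.92-4.95% | about 2.5% |
| 0.3 | 3.61-3.63% | 4.77-4.80% | about 2.5% |
| 0.5 | 3.45-3.49% | 4.52-4.56% | about 2.5% |
| 0.8 | 3.05% | 3.90-3.91% | about 2.5% |

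**Step 5: how far the excess reaches.** S2-level interval, correlation 0 to 0.3:
- Toric truly worse by 0.005 logMAR: 2.65-2.73%.
- Worse by 0.010: 2.51-2.53%.
- Worse by 0.015, the smaller difference in Table 10: no different from S3 alone.
- Preference truly non-null (S3 power 0.85 to 0.99), difference 0: false superiority 2.2-2.5%, within the benchmark.

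**The case against.** The strongest case against is that the point is narrow. A material excess needs P1 and S1 met, preference truly null even though toric has just won on acuity and on CLUE vision, and toric almost exactly equal to spectacles. Table 7, from a different lens pair, shows 68.1% against 23.6% preferring the toric lens, which makes a null preference look unlikely. Study success rests on the primary hypothesis alone. All of this stands and limits the size. It does not restore the control, because study-wise control has to hold for every combination of true nulls, including this one.

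A second objection is that the plan declares only favourable results, so the chance of a false declared claim stays at or below 5% on either reading of the interval. That is correct as arithmetic. But the plan's own rule for P1 allows 2.5% in the tested direction, and the added claim should be judged on the same scale.

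A third is that the opening rule of section 14.6 already gives superiority to ITT. That is a fair reading. The population point only needs reconciling and adds nothing to the alpha argument.

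Three stronger readings are not supported. A reader might infer that superiority follows automatically from non-inferiority; section 14.6 also requires the interval to lie below zero. A reader might double the bound and speak of a 7.5% false-claim rate; that counts an unfavourable tail in which the plan makes no claim. A reader might say Figure 2 is known to lack a node for this test; the figure is not available, and its absence is inferred from the caption and the reference to Holm.

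**Conclusion.** The point holds, at modest size. Nothing in the documents conditions superiority over spectacles on S3 or gives it a place in the alpha propagation, so the control promised in section 14.4 does not extend to it. Against the inferred 2.5% benchmark, the chance of at least one false claim is about 3.6-3.7% at correlation 0 to 0.3, 3.05% at 0.8 and at most 3.75%. It can reach 5% if superiority is read from a 95% interval, which the text does not rule out. These figures are near the worst case: they assume P1 and S1 met, preference truly null and toric truly equal to spectacles.

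A reader might take this as a fault in the main results. It is not: the tests of P1, S1, S2 and S3 keep their stated error rates, and the order non-inferiority then superiority is not itself at fault. The plan should be corrected before database lock so that the claim is not reported as error-controlled.

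**What to change.** **Preferred.** In section 14.6, state that superiority over spectacles is read from the ITT interval, in line with that section's opening rule, and is reported descriptively, outside the section 14.4 error control. This takes one sentence. The cost is the confirmatory claim; S2 and S3 lose no power.

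**Alternative, if the sponsor wants a confirmatory claim.** Add superiority over spectacles as a final node, tested at two-sided 0.05 on ITT only after S2 and S3 are both rejected, with matching edits to section 2.3, the synopsis and Figure 2 with its caption. The simulated error returns to 2.5%, and S2 and S3 again lose nothing, but the acuity claim then depends on the preference result. At an assumed true difference of −0.02 logMAR, ICC 0.3 to 0.5, superiority power changes as follows:
- S3 power 0.85 (about Table 11's level for a proportion difference of 0.24 at 0.05): from 0.62-0.76 as written to 0.55-0.69. The as-written range is 0.63-0.77 if the S2 interval is also taken as 95% when S3 is rejected in the second Holm step.
- S3 power 0.983 (Table 11, difference 0.32 at 0.05): from 0.64-0.78 to 0.63-0.78.
- Preference truly null: from about 0.53-0.69 to about 0.02 (0.025 × 0.64 to 0.79, independent tests).

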14.7. Other Exploratory Analysis

Not applicable.

14.8. Interim Analysis

Not applicable.

14.9. Procedure for Handling Missing Data and Drop-Outs

Missing or spurious values will not be imputed. The count of missing values will be included in the summary tables and listings.

14.10. Procedure for Reporting Deviations from Statistical Plan

The analysis will be conducted according to that specified in above sections. There are no known reasons for which it is planned to deviate from these analysis methods. If for any reason a change is made, the change will be documented in the study report along with a justification for the change.

Clinical Study Protocol

Johnson & Johnson Vision Care, Inc.

15. DATA HANDLING AND RECORD KEEPING/ARCHIVING

15.1. Electronic Case Report Form/Data Collection

The data for this study will be captured on electronic case report forms (eCRFs) using the BioClinica EDC system. An authorized data originator will enter study data into the eCRFs using the EDC system. Data collected on equipment that is not captured in EDC will be formatted to the specification of the JJVC database manager and sent to JJVC for analysis.

No external data sources will be included in this study.

The clinical data will be recorded on dedicated eCRFs specifically designed to match the study procedures for each visit. Only specifically delegated staff can enter data on a CRF. Once completed, the eCRFs will be reviewed for accuracy and completeness and signed by the Investigator. The sponsor or sponsor's representatives will be authorized to gain access to the subject recordation for the purposes of monitoring and auditing the study.

Edit checks, electronic queries, and audit trails are built into the system to ensure accurate and complete data collection. Data will be transmitted from the clinical site to a secure central database as forms are completed or updated, ensuring information accuracy, security, and confidentiality. After the final database lock, the Investigator will be provided with Individual Patient Profiles (IPP) including the full audit trail on electronic media in PDF format for all of the study data. The IPP must be retained in the study files as a certified copy of the source data for the study.

The content and structure of the eCRFs are compliant with ISO14155:2020.¹

15.2. Subject Record

At a minimum, subject record should be available for the following:

- subject identification
- eligibility
- study identification
- study discussion
- provision of and date of informed consent
- visit dates
- results of safety and efficacy parameters as required by the protocol
- a record of all adverse events
- follow-up of adverse events
- medical history and concomitant medication
- test article receipt/dispensing/return records
- date of study completion
- reason for early discontinuation of test article or withdrawal from the study, if applicable

Clinical Study Protocol

Johnson & Johnson Vision Care, Inc.

The subject record is the eCRF or an external record. The author of an entry in the subject record must be identifiable. The first point of entry is considered to be the source record.

Adverse event notes must be reviewed and initialed by the Investigator.

15.3. Trial Registration on ClinicalTrials.gov

This study will be registered on ClinicalTrials.gov by the Sponsor.

16. DATA MANAGEMENT

16.1. Access to Source Data/Document

The Investigator/Institution will permit trial-related monitoring, audits, IEC/IRB review and regulatory inspection(s) by providing direct access to source data/documents. Should the clinical site be contacted for an audit by an IEC/IRB or regulatory authority, JJVC must be contacted and notified in writing within 24 hours.

16.2. Confidentiality of Information

Information concerning the investigational product and patent application processes, scientific data or other pertinent information is confidential and remains the property of JJVC. The Investigator may use this information for the purposes of the study only. It is understood by the Investigator that JJVC will use information developed in this clinical study in connection with the development of the investigational product and therefore may disclose it as required to other clinical investigators and to regulatory agencies. In order to allow the use of the information derived from this clinical study, the Investigator understands that he/she has an obligation to provide complete test results and all data developed during this study to the Sponsor.

16.3. Data Quality Assurance

Steps will be taken to ensure the accuracy and reliability of data, include the selection of qualified investigators and appropriate clinical sites and review of protocol procedures with the Principal Investigator. The Principal Investigator, in turn, must ensure that all Sub-Investigators and clinical site personnel are familiar with the protocol and all study-specific procedures and have appropriate knowledge of the study article.

Training on case report form completion will be provided to clinical site personnel before the start of the study. The Sponsor will review case report forms for accuracy and completeness remotely during the conduct of the study, during monitoring visits, and after transmission to data management. Any data discrepancies will be resolved with the Investigator or designee, as appropriate.

Quality Assurance representatives from JJVC may visit clinical sites to review data produced during the study and to access compliance with applicable regulations pertaining to the conduct of clinical trials. The clinical sites will provide direct access to study-related source

Clinical Study Protocol

Johnson & Johnson Vision Care, Inc.

data/documents and reports for the purpose of monitoring and auditing by JJVC and for inspection by local and regulatory authorities.

16.4. Data Monitoring Committee (DMC)

Not applicable for this study.

17. CLINICAL MONITORING

The study monitors will maintain close contact with the Principal Investigator and the Investigator's designated clinical site personnel. The monitor's responsibilities will include:

- Ensuring that the investigation is being conducted according to the protocol, any subsequent versions, and regulatory requirements are maintained.
- Ensuring the rights and wellbeing of subjects are protected.
- Ensuring adequate resources, including facilities, laboratories, equipment, and qualified clinical site personnel.
- Ensuring that protocol deviations are documented with corrective action plans, as applicable.
- Ensuring that the clinical site has sufficient test article and supplies.
- Clarifying questions regarding the study.
- Resolving study issues or problems that may arise.
- Reviewing of study records and source documentation verification in accordance with the monitoring plan.

18. ETHICAL AND REGULATORY ASPECTS

18.1. Study-Specific Design Considerations

Potential subjects will be fully informed of the risks and requirements of the study and, during the study, subjects will be given any new information that may affect their decision to continue participation. Subjects will be told that their consent to participate in the study is voluntary and may be withdrawn at any time with no reason given and without penalty or loss of benefits to which they would otherwise be entitled. Subjects will only be enrolled if the fully able to understand the risks, benefits, and potential adverse events of the study and provide their consent voluntarily.

